#### 5.2.3. Pharmacodynamic Endpoints

The WBC cystine content will be measured from samples collected 0.5 hour post dose at each study visit.

[REDACTED]

[REDACTED]  
[REDACTED]  
[REDACTED]

## 6. Overall Study Design and Plan

### 6.1. Study Design

This is a long-term, open-label Study of the safety, tolerability and steady-state pharmacokinetics and pharmacodynamics of RP103 in pediatric and adult patients with cystinosis. Initially only patients who completed the previous phase III Study RP103-03 will be offered the opportunity to enroll in this extension Study.

Additional patients who did not complete Study RP103-03 but qualify for RP103-04 based on current inclusion and exclusion criteria may be enrolled after completion of the analysis of the RP103-03 Study where the non-inferior efficacious and safe dose of RP103 versus Cystagon® has been determined.

#### 6.1.1. Study Visits

For patients who completed Study RP103-03, study visits consist of:

- Screening Visit: The RP103-04 Screening visit occurs simultaneously with the RP103-03 Period 2 Day 7 (End of Study) visit. These patients will continue RP103 Q12H treatment at the last dose level prescribed during their participation in Study RP103-03.
- Monthly Study Visits are only for patients who completed Study RP103-03 and will begin within 1 month ( $\pm$  7 days) after study entry. Each patient will complete a minimum of 6 consecutive Monthly visits.
- Quarterly Study Visits will commence for each patient  $\geq$  1 month and  $<$  4 months after the patient has completed at least 6 consecutive Monthly visits. Each Quarterly visit will take place by the middle of the first month ( $\pm$  7 days) of each calendar quarter (i.e., January 15, April 15, July 15 and October 15).
- End of Study (EOS) Visit will be conducted within 7 ( $\pm$  2 days) from the last completed study visit or from the date of decision to terminate.

For patients who did not complete Study RP103-03, study visits consist of:

- Screening Visit which may occur up to 28 days prior to Day 1.
- Dose Confirmation Period (Days 1-5) which includes 3 study visits over 5 days.
  - Day 1 includes a morning study visit while the patient is fasted, with pre-dose blood samples collected for trough cysteamine and peak WBC cystine determination while the subject is still taking Cystagon®. RP103 treatment regimen begins at the clinic on the morning of Day 1, administered Q12H at a starting total daily RP103 dose equal to 70% of the Screening total daily Cystagon® dose. Patients will leave the clinic for Days 2-3 and take RP103 as instructed.

- Days 4 and 5 each include a morning study visit; RP103 Q12H treatment regimen continues.
- Quarterly Study Visits will commence for each patient by the middle of the first month ( $\pm$  7 days) of each calendar quarter (i.e., January 15, April 15, July 15 and October 15).
- End of Study (EOS) Visit will be conducted within 7 ( $\pm$  2 days) from the last completed study visit or from the date of decision to terminate.

#### 6.1.2. Study Procedures

For patients who completed Study RP103-03, study procedures include:

##### **Screening**

The RP103-04 Screening visit occurs simultaneously with the RP103-03 Period 2 Day 7 (End of Study) visit. These patients will continue RP103 Q12H treatment at the last dose level prescribed during their participation in RP103-03.

##### **Monthly Study Visits**

Only patients who completed Study RP103-03 will attend Monthly Visits. These visits will be made monthly ( $\pm$  7 days) after study entry according to the Schedule of Events, Appendix 14.1. A minimum of six (6) consecutive Monthly visits will be completed for each patient. Clinical laboratory assessments (hematology, chemistry, urinalysis), physical examination (including basic neurological and skin assessments) and vital signs, ECG, body weight, body mass index (BMI), body surface area (BSA), an Investigator administered [REDACTED]

[REDACTED] will be made according to the Schedule of Events. During these visits, blood samples for PK (cysteamine) and PD (WBC cystine) will be collected 0.5 hour post RP103 dose administered at the clinic. Patients or parents will continue to maintain a daily diary, recording the dose and time, of cysteamine medications, proton pump inhibitors (PPI) and other gastric acid reducing drugs (prescription and over the counter medications). Patients or their parents will return their completed daily diary at each scheduled study visit and will receive a new or re-dispensed daily diary. Concomitant medications and adverse events will be collected.

At or before each Monthly Visit, the Investigator will review available safety and PK/PD data and if a patient does not achieve an appropriate level of WBC cystine reduction or does not tolerate the dose, the patient may have their RP103 dose adjusted or may be terminated from the study. This review will be documented in source and in the CRF as appropriate, with the action(s) taken and reasons for such action(s).

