Based on these experiments, it was determined that the Lowry vs. BCA protein results had to be adjusted as follows:

$$\text{protein amount[Lowry]} = \text{protein amount[BCA]} * 1.6999 - 0.0648$$

The correction factor ensures the patients participating in the study to receive a safe and appropriate dose of RP103 in an effort to get their WBC cystine levels similar to levels reported historically (prior to their enrollment in Raptor's clinical studies). This also allows WBC cystine results reported from the clinical studies to be consistent with all previous clinical trials and surveys, as well as with previous Cystagon® guidelines.

Regular Q6H daily treatment with Cystagon® has been shown to diminish the rate of renal dysfunction as well as promoting improved growth in children with cystinosis (Kleta, Bernardini et al. 2004). Current guidelines for following WBC cystine levels are based on obtaining blood 5 to 6 hours after the last dose of Cystagon® (Schneider 2004). White blood cell (WBC) cystine content rapidly decreases after Cystagon® ingestion, but can return to predose levels within 6 hours (Smolin, Clark et al. 1988).

RP103 dose will then be increased by approximately 10% on regular time intervals until the WBC cystine level is < 1 nmol ½ cystine/mg protein or until the patient experiences some tolerability issue.

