##### **Quarterly Study Visits**

Quarterly visits will commence for each patient  $\geq$  1 month and  $<$  4 months after the patient has completed 6 consecutive Monthly visits. Each Quarterly visit will take place

by the middle of the first month ( $\pm$  7 days) of each calendar quarter (i.e., January 15, April 15, July 15 and October 15). Clinical laboratory assessments, clinical laboratory assessment (hematology, chemistry, urinalysis), physical examination (including basic neurological and skin assessments) and vital signs, ECG, body weight, body mass index (BMI), body surface area (BSA), [REDACTED]

[REDACTED] [REDACTED] will be made according to the Schedule of Events.

During these visits, blood samples for PK (cysteamine) and PD (WBC cystine) will be collected 0.5 hour post RP103 dose administered at the clinic. Patients or parents will continue to maintain a daily diary, recording the dose and time, of cysteamine medications, proton pump inhibitors (PPI) and other gastric acid reducing drugs (prescription and over the counter medications). Patients or their parents will return their completed daily diary at each scheduled study visit and will receive a new or re-dispensed daily diary. Concomitant medications and adverse events will be collected.

At or before each Quarterly Visit, the Investigator will review available safety and PK/PD data and if a patient does not achieve an appropriate level of WBC cystine reduction or does not tolerate the dose, as determined by the Investigator, the patient may have their RP103 dose adjusted or may be terminated from the Study. This review will be documented with the action(s) taken and reasons for such action(s).

For patients who did not complete Study RP103-03, study procedures include:

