### **8.5. Study Treatment Administration and Compliance**

All study treatments administered in the clinic will be under the supervision of clinic personnel. Patients not entering the trial from Study RP103-03 will be started on twice a day administration of RP103, where the total daily RP103 dose is 70% of their total daily stable Cystagon® dose.

If during the study any patient does not achieve a meaningful reduction of WBC cystine level (i.e., < 1 nmol ½ cystine/mg protein) or does not tolerate the dose, as determined by the Investigator, the patient may have their RP103 dose adjusted or may be terminated from the study.

A daily diary of cysteamine and gastric acid reducing medications will be maintained throughout the study.

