### **11.5. Accountability Procedure**

Missing values will not be imputed.

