#### 4.2.4. Adjustments for Covariates

There are no planned adjustments for covariates in this study.

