#### 4.2.8. Missing, Unused and Spurious Data

Imputation of missing data is not planned.

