## 8. PHARMACOKINETIC, PHARMACODYNAMIC AND

### 8.1. Pharmacodynamics

WBC cystine concentration levels (nmol  $\frac{1}{2}$  cystine/mg) will be summarized over time using descriptive statistics (number of subjects, mean, geometric mean, median, standard deviation, coefficient of variation, minimum, and maximum) for the PK/PD Population for each subpopulation and overall. Summaries will be provided for both analysis visits and collected visits. WBC cystine concentration levels will also be summarized over time by baseline WBC cystine levels ( $\leq 1$ ,  $> 1$  to  $\leq 2$ ,  $> 2$  nmol  $\frac{1}{2}$  cystine/mg) for both analysis visits and collected visits.

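### By-visit WBC cystine means may be biased downward by selective exit, and the visible SAP has no analysis that separates this from a titration effect or bounds it

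*Protocol*

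**What the plan says.** **Exit.** Protocol 6.1.2 has the Investigator review safety and PK/PD data at or before each Monthly visit. A patient without an appropriate WBC cystine reduction, or who does not tolerate the dose, "may have their RP103 dose adjusted or may be terminated from the study". The Quarterly text says the same for both entry routes: "as determined by the Investigator, the patient may have their RP103 dose adjusted or may be terminated from the Study". Protocol 8.5 gives the threshold, referring to a patient who "does not achieve a meaningful reduction of WBC cystine level (i.e., < 1 nmol ½ cystine/mg protein". Sections 9.1.4 and 9.1.5 repeat it. Protocol 4.5 describes the other route: "RP103 dose will then be increased by approximately 10% on regular time intervals until the WBC cystine level is" below 1, or until tolerability limits it.

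**Analysis.** Under SAP 8.1, WBC cystine levels "will be summarized over time using descriptive statistics", by analysis visit and by collected visit, overall, by subpopulation and by baseline WBC cystine category. Figure 1 (SAP 12.3) plots mean and SD by collected visit. On missing data, SAP 4.2.8 says "Imputation of missing data is not planned" and Protocol 11.5 says "Missing values will not be imputed". SAP 4.2.4 adds: "There are no planned adjustments for covariates in this study". SAP 3.1 keeps anyone with at least one PK/PD measurement, and SAP 4.2.7 plans no exclusions for withdrawal.

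The SAP does not use the term observed cases. That each visit mean covers only patients with a value at that visit follows from by-visit descriptive statistics without imputation.

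**The concern.** The variable that can trigger a patient's removal is the variable being averaged. If patients with persistently high values are the ones who leave, the mean of those remaining falls even when no individual changes. Dose escalation in patients who stay also lowers the mean, and that is a real effect of treatment. The planned tables and figure show the two mixed together.

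What is at stake is how the long-term pharmacodynamic result is read. Treatment may last up to about 96 months (Protocol 6.3) in at most 60 patients (Protocol synopsis), so a few exits can matter at late visits. A flat or falling curve would naturally be read as sustained control of WBC cystine on RP103. The plan as visible gives no way to judge how much of that curve is composition.

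**Working it through.** The documents state no removal rate, dropout rate or within-patient correlation, so there is no planned figure to reproduce. I checked the mechanism, then the sensitivity.

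**1. Sensitivity in the protocol's own data (Protocol 4.2.2, Table 3).** Three of 41 patients (3/41 = 7%) were left out of the per-protocol analysis because their average level exceeded 2 in a Cystagon period.
- RP103 LS mean: 0.70 with them, 0.62 without. 1 - 0.62/0.70 = 11%.
- Treating LS means crudely as arithmetic means, the three averaged (41 × 0.70 - 38 × 0.62)/3 = 1.7 on RP103.

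**2. One-off removal, no true change.** Assume lognormal values with mean 0.63 and SD 0.31 (Protocol Table 2, per-protocol baseline). The RP103 LS-mean SE gives a similar SD: 0.05 × √38 = 0.308.
- Log-scale variance: ln(1 + (0.31/0.63)²) = 0.217, so SD 0.466 and mean ln(0.63) - 0.108 = -0.570.
- Share above 1: 1 - Φ(0.570/0.466) = 11%.
- Removing 10, 25, 50 or 100% of those above 1 moves the observed mean from 0.63 to 0.623, 0.612, 0.592 or 0.550 (at most -13%).
- With all removed, the median moves from exp(-0.570) = 0.565 to exp(-0.570 + 0.466 × Φ⁻¹(0.445)) = 0.530 (-6%).

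**3. Repeated removal, no true change.** This is a simulation of 200,000 patients over 20 quarterly visits with the same distribution. Each visit with a value above 1 carries a removal probability f. Both f and the within-patient correlation (log scale, 0.3 to 0.7) are assumptions.

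| f per uncontrolled visit | Observed mean at visit 20 | Change from 0.63 |
|---|---|---|
| 0 | 0.63 | 0 |
| 2% | 0.625 to 0.612 | -1 to -3% |
| 10% | 0.598 to 0.567 | -5 to -10% |
| 25% | 0.567 to 0.527 | -10 to -16% |

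With zero within-patient correlation the mean does not move at any f.

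A wider distribution gives larger shifts (to -54%), using an SD of 0.19 × √41 = 1.22 derived from the intention-to-treat SE. I do not rely on these. That SE is the same for both treatments and comes from a model. On the crude basis of step 1, the three patients' RP103 values total 5.14. The most extreme split (one at 5.14, two at 0) gives a variance of (38 × 0.62² + 37 × 0.31² + 5.14² - 41 × 0.70²)/40 = 0.61, so an SD of about 0.8.

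**4. Can the planned output tell selection from titration?** At f = 10% and correlation 0.5, the mean at visit 20 is 0.580 with 83% of patients remaining. A true 8% fall in every patient (0.63 × 0.92 = 0.580), with 17% leaving for unrelated reasons, gives the same mean and the same N. A shrinking spread or maximum does not settle it, because titration directed at patients above 1 also trims the upper tail.

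**The case against.** The strongest case against has five parts.

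- **Termination is optional.** Dose adjustment is named first, and Protocol 4.5 describes stepwise increases. In RP103-03 about two-thirds of patients who started at 70% had their dose raised (Protocol 4.2.2). Patients also leave by request, sponsor decision or marketing approval (Protocol 6.3), and the withdrawal list in Protocol 7.3 does not name inadequate WBC cystine. This stands. A reader might infer that late means will improve through selection, or that they describe responders only. The documents do not support either: they give no removal rate, and uncontrolled patients can stay and be titrated.
- **The RP103-03 comparison is an analogy.** Those three patients were not terminated, and they were selected on Cystagon values. This stands. A reader might also cite the Cystagon LS mean, which drops from 0.97 to 0.54 (1 - 0.54/0.97 = 44%). That figure is selected and measured on the same comparator values, so it says nothing direct about a single-arm RP103 study.
- **The SAP has safeguards.** It plans N, median, minimum and maximum per visit, baseline strata, discontinuation counts by reason (SAP 5), retained pre-exit values and an End of Study sample. These show that patients leave. They do not link exit to on-treatment cystine: the strata use baseline values, and SAP 5 does not connect reasons to levels. The median is less affected but still moves.
- **Text is redacted.** Parts of SAP 8 and the table list in SAP 12 are blacked out. This stands, so the claim covers visible text only.
- **The measure is secondary and descriptive.** The primary objective is safety, and the synopsis also lists cysteamine concentration as an efficacy parameter. This limits the stakes but does not remove the ambiguity in the long-term curve.

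**Conclusion.** The concern holds as a risk that the plan neither shows nor bounds. Exit may depend on WBC cystine, and WBC cystine is then averaged over patients who still have a value. The bias would run downward if patients with persistently high values are removed.

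Its size cannot be stated. The only figure in the documents that bears on RP103 is the 11% shift from leaving out 3 of 41 patients, which is an illustration and not a forecast. Under the assumed removal rates of 2 to 25% per uncontrolled visit and within-patient correlations of 0.3 to 0.7, the shift over 20 quarters is -1 to -16%. It is zero if nobody is removed for cystine or if values are uncorrelated within patients. The stronger conclusion, that observed long-term control is an artefact of selection, is not supported. The safety objective is not affected.

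**What to change.** Add to SAP 8.1, before the final database lock:

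1. **Last on-RP103 WBC cystine value** for every treated patient with a value, overall and by reason for leaving. Exclude End of Study samples taken after return to Cystagon. Protocol 6.1.2 has these drawn before the next Cystagon dose, and the date-based windows in SAP 4.2.9 do not visibly exclude them.
2. **By study year, the percentage below 1 nmol ½ cystine/mg protein**, with numerators and denominators and a stated choice of value within the year. Patients terminated for inadequate WBC cystine reduction are carried as not controlled. Intolerance exits are shown separately. Patients who left for marketing availability, sponsor decision or other unrelated reasons count only for the years they were followed. This leans conservative in late years, because unrelated exits shrink the denominator while carried patients stay in it; a footnote should say so.
3. **The by-visit table and Figure 1 repeated in the fixed cohort still on RP103 at a pre-stated late visit**, labelled as describing retained patients. Composition is then constant over time, and the gap between all patients and this cohort at early visits shows how far those retained differ.

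The cost is a few descriptive tables from collected data, with no modelling. The reported long-term control rate may be slightly lower. One check is needed: if the eCRF discontinuation categories do not identify inadequate WBC cystine reduction, the reason must be taken from the documented Investigator reviews that Protocol 6.1.2 already requires.

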##### **Quarterly Study Visits**

Quarterly visits will commence for each patient  $\geq$  1 month and  $<$  4 months after the patient has completed 6 consecutive Monthly visits. Each Quarterly visit will take place

by the middle of the first month ( $\pm$  7 days) of each calendar quarter (i.e., January 15, April 15, July 15 and October 15). Clinical laboratory assessments, clinical laboratory assessment (hematology, chemistry, urinalysis), physical examination (including basic neurological and skin assessments) and vital signs, ECG, body weight, body mass index (BMI), body surface area (BSA), [REDACTED]

[REDACTED] [REDACTED] will be made according to the Schedule of Events.

During these visits, blood samples for PK (cysteamine) and PD (WBC cystine) will be collected 0.5 hour post RP103 dose administered at the clinic. Patients or parents will continue to maintain a daily diary, recording the dose and time, of cysteamine medications, proton pump inhibitors (PPI) and other gastric acid reducing drugs (prescription and over the counter medications). Patients or their parents will return their completed daily diary at each scheduled study visit and will receive a new or re-dispensed daily diary. Concomitant medications and adverse events will be collected.

At or before each Quarterly Visit, the Investigator will review available safety and PK/PD data and if a patient does not achieve an appropriate level of WBC cystine reduction or does not tolerate the dose, as determined by the Investigator, the patient may have their RP103 dose adjusted or may be terminated from the Study. This review will be documented with the action(s) taken and reasons for such action(s).

For patients who did not complete Study RP103-03, study procedures include:

### **Screening**

The Screening visit may occur up to 28 days prior to Day 1.

Medical and medication histories and clinical laboratory assessment (hematology, chemistry, urinalysis), physical examination (including basic neurological and skin assessments) and vital signs, ECG, body weight, body mass index (BMI), body surface area (BSA), adverse events determination, concomitant medications, an Investigator administered [REDACTED]

[REDACTED] will be made according to the Schedule of Events, Appendix 14.1.

All adult patients or parent or guardian of pediatric patients will begin completing a daily diary medication log, recording the dose and time, of cysteamine medications, proton pump inhibitors (PPI) and other gastric acid reducing drugs (prescription and over the counter medications).

### **Dose Confirmation Period (Days 1-5)**

This period entails 3 study visits over 5 days, required only for patients that did not complete Study RP103-03.

- **Day 1:** If this visit is more than 7 days after the Screening date, some assessments must be repeated as specified in the Schedule of Events. This is a morning study visit while the patient is fasted, with pre-dose (within 15 minutes

prior to the first RP103 dose) blood samples collected for trough cysteamine and peak WBC cystine determination while the subject is still taking Cystagon®. RP103 treatment regimen begins at the clinic on the morning of Day 1, administered Q12H at a starting RP103 total daily dose equal to 70% of the Screening total daily dose of Cystagon®.

- **Days 4 and 5:** Each day includes a morning visit. 0.5 hour (30 minute) post-dose blood samples for plasma cysteamine (PK) and WBC cystine (PD) determination will be collected. RP103 Q12H treatment regimen continues at the starting total daily dose. Once the Investigator receives WBC cystine results for the Dose Confirmation Period, and RP103 dose adjustment may be prescribed so that it can be implemented before the subject returns for their next study visit (Quarterly Visit 1).

### **Quarterly Study Visits**

Quarterly visits will take place by the middle of the first month ( $\pm$  7 days) of each calendar quarter (i.e., January 15, April 15, July 15 and October 15). Clinical laboratory assessments, clinical laboratory assessment (hematology, chemistry, urinalysis), physical examination (including basic neurological and skin assessments) and vital signs, ECG, body weight, body mass index (BMI), body surface area (BSA), an Investigator administered [REDACTED]

[REDACTED] will be made according to the Schedule of Events.

During these visits, blood samples for PK (cysteamine) and PD (WBC cystine) will be collected 0.5 hour post RP103 dose administered at the clinic. Patients or parents will continue to maintain a daily diary, recording the dose and time, of cysteamine medications, proton pump inhibitors (PPI) and other gastric acid reducing drugs (prescription and over the counter medications). Patients or their parents will return their completed daily diary at each scheduled study visit and will receive a new or re-dispensed daily diary. Concomitant medications and adverse events will be collected.

At or before each Quarterly Visit, the Investigator will review available safety and PK/PD data and if a patient does not achieve an appropriate level of WBC cystine reduction or does not tolerate the dose, as determined by the Investigator, the patient may have their RP103 dose adjusted or may be terminated from the Study. This review will be documented in source and in the CRF as appropriate, with the action(s) taken and reasons for such action(s).

